### Pivot Breath Sensor.

The primary endpoint will assess any change in the proportion of participants' Stage of Change response at day 28 compared to baseline

- A positive outcome is defined as a participant responding as more ready to quit. For example, a change in response from seriously thinking of quitting smoking "...within the next 6 months" at baseline to seriously thinking of quitting smoking "...within the next 30 days" at day 28.

The secondary endpoints include:

- The proportion of participants who reported  $\geq 1$  quit attempt by day 28; will be compared to zero
  - A quit attempt is defined as answering  $\geq 1$  to the following question: "Since you began using the Pivot Breath Sensor, how many times have you tried to quit smoking where you've gone at least 1 day without smoking a cigarette, even a single puff?"
- The proportion of participants who reduced their cigarettes per day (CPD) by  $\geq 50\%$  by day 28, compared to baseline

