#### Inclusion Criteria

- 18-80 years of age
- Current daily cigarette smokers (at least 10 cigarettes per day)
- Resident of the United States
- Able to read and comprehend English
- Owns and uses a smartphone compatible with the study app (iPhone 5 and above, operating system iOS 11 and above, or, Android 5.0 and above, operating system Android 5.0 and above)
- Willing to sign the Informed Consent Form

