## **6.6 SAMPLE SIZE AND JUSTIFICATION**

This study will enroll up to 220 participants. Consideration for the sample size included powering the study to observe a clinically meaningful change from baseline for the primary and secondary endpoints using 80% power at a statistical significance of  $P < 0.05$ . The primary endpoint utilized preliminary data from a similar 37 participant pilot study. Data at the 14-day time point showed 31%, 66% and 3% of participants had increased, unchanged and decreased Stage of Change, respectively, from baseline. To detect a statistically significant change in these proportions requires enrolling 50 participants.

The estimated proportion of participants achieving  $\geq 1$  quit attempt is 25% based on interim results from the pilot study. Based on the median prevalence of 65.4% for past-year quit attempts in the general population [13], the average monthly quit attempt rate is approximately 5%. To show that a proportion of 25% of participants making a quit attempt by day 28 is statistically different from 5% will require  $n=16$ .

Finally, literature indicates approximately 1% of the general population [14-18] and 2-5% of individuals in cigarette reduction studies [19, 20] will reduce their CPD by  $\geq 50\%$  on a monthly basis. Assuming that 10% of participants in the present study reduce their CPD by  $\geq 50\%$  by day 28, the present study will require  $n=185$  to show a difference from 5%. Taking these analyses into consideration along with expected attrition, the present study will enroll up to 220 participants.

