## 10.2 ANALYSIS

Changes in measurements from baseline will be assessed at different timepoints in the study. Participants will serve as their own controls and comparisons will be made to no change. One sample t-test will be used for numerical data. Fisher's Exact or Chi square tests will be used for categorical data. Analyses will be conducted to calculate mean (SD) for normally distributed variables for actual data or mean (SE) for modeled data and median (interquartile range) values in instances of non-normally distributed variables.

McNemar test will be used for 2-category match-paired data. Cohen kappa statistic will be used for 3-category match-paired data. To evaluate changes in attitudes or cigarettes smoked per day over time, repeated measures linear mixed model analyses will be performed using a compound symmetric correlation matrix to model the repeated measures within subjects. To make specific comparisons across time, F statistics will be computed using the results from the model. Statistical significance is set at  $P < .05$ .

Analyses for the outcomes will be evaluated for only those who complete the survey (i.e. completer) and assessed to take into account missing data. To be included in any completer analysis the participant must provide a baseline response and the outcome response. For outcomes that are missing data, these will be assessed pending the data type.

For categorical data, the last response post-baseline will be carried forward for the day 28 analysis and the last response post-28 days will be carried forward for the day 84 assessment. If there is not any data to carry forward, the data will be considered unchanged from baseline. Numerical data will use linear mixed modeling.

All deviations from the study protocol will be identified, recorded and analyzed.

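### The ≥50% CPD-reduction endpoint is sized against a 5% reference rate, but the analysis text gives it only baseline, where the rate is 0% by definition; quit attempts have the same mismatch

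*Combined protocol and SAP*

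**What the plan says.** Three places bear on the CPD endpoint.

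- **Section 6.3, secondary endpoints.** The endpoint is "The proportion of participants who reduced their cigarettes per day (CPD) by" at least 50% "by day 28, compared to baseline". No reference proportion is given. The bullet above it, on quit attempts, does give one: the proportion with at least one "quit attempt by day 28; will be compared to zero".
- **Section 6.6, sample size.** "Assuming that 10% of participants in the present study reduce their CPD by" at least 50% by day 28, the plan asks for n=185 "to show a difference from 5" per cent. It cites monthly background rates of about 1% in the general population and 2–5% in cigarette-reduction studies. Quit attempts are sized as 25% against 5% (n=16).
- **Section 10.2, analysis.** "Changes in measurements from baseline will be assessed at different timepoints in the study", and then: "Participants will serve as their own controls and comparisons will be made to no change". The tests named for categorical data are Fisher's exact or chi-square, with McNemar for paired two-category data. No external reference rate appears.

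Section 6.3 also lists 7-day and 30-day abstinence as outcomes. Entry is limited to "Current daily cigarette smokers (at least 10 cigarettes per day"), and the schedule in 7.7 first collects abstinence at day 14.

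**The concern.** A no-change null makes sense for mean CPD or an attitude score. It means little for the proportion who have halved their CPD since baseline, because that proportion is 0% at baseline whatever the device does. A test against that value asks only whether anyone cut down by half. Section 6.6 accepts that some smokers do so without the device, which is why it sizes the endpoint against 5%.

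This endpoint sets the size of the study: the other two calculations need 50 and 16 participants. There is no concurrent control group, so a fixed external rate is the only thing separating a device effect from background change on this endpoint. If the analysis drops that rate, a result no better than the plan's own background range could be reported as significant.

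**Working it through.** **Inputs.** From 6.6: null rate 5%, assumed rate 10%, 80% power, significance at 0.05, n=185, enrolment up to 220, background rates 1% and 2–5%. From 10.2: comparison to no change, with McNemar, Fisher or chi-square tests. Sidedness is not stated; two-sided is assumed because it reproduces n=185.

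**1. Reproduce the plan's figures.** For a one-sample proportion test (normal approximation),

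n = [z(0.975)·√(p0(1−p0)) + z(0.80)·√(p1(1−p1))]² / (p1−p0)²

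- CPD, p0=0.05, p1=0.10: (1.960×√0.0475 + 0.842×√0.09)² / 0.05² = (0.4272 + 0.2525)² / 0.0025 = 184.77, so 185. This matches. One-sided gives 150, a continuity correction gives 205, and a two-sample comparison gives 435 per arm.
- Quit attempts, p0=0.05, p1=0.25: (0.4272 + 0.3644)² / 0.04 = 15.67, so 16. This also matches.

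Both calculations therefore use a one-sample test against 5%.

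**2. Threshold under no change.** With every participant a non-responder at baseline, all x responders are discordant in one direction. Exact McNemar gives P = 2×0.5^x.

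- x=5: 0.0625, not significant.
- x=6: 0.031, significant.

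Six responders are 6/185 = 3.2% or 6/220 = 2.7%. Fisher's test of 6 against 0 gives P=0.030 at either size, although it treats the same people as two independent groups. McNemar chi-square without correction needs only 4.

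**3. Threshold against 5%.**

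| n | Test | Responders needed | Upper-tail error at true 5% | Power at true 10% |
|---|---|---|---|---|
| 185 | exact or z | 16 (8.6%) | 0.024 | 0.764 |
| 220 | z | 18 (8.2%) | 0.029 | 0.845 |
| 220 | exact (doubled tail) | 19 (8.6%) | 0.015 | 0.781 |

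At n=185, a count of 6 to 15 (3.2% to 8.1%) is significant under the no-change test but not under the hypothesis in 6.6.

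**4. Chance of significance under no change.** This is the binomial probability of at least 6 responders:

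| True rate | n=185 | n=220 |
|---|---|---|
| 1% | 0.011 | 0.024 |
| 2% | 0.168 | 0.279 |
| 3% | 0.481 | 0.649 |
| 5% | 0.904 | 0.966 |

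**5. Quit attempts.** The comparison to zero is written out in 6.3. The count runs from the start of sensor use, so it too begins at zero by construction, and step 4 applies unchanged: at the 5% monthly rate that 6.6 derives, at least 6 positive answers occur with probability 0.90 (n=185) or 0.97 (n=220).

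**The case against.** The strongest reply is that no passage says the CPD endpoint is tested against zero. The baseline phrase in 6.3 can be read as defining the reduction and not as a null proportion. The only numerical hypothesis for the endpoint is the one in 6.6, and the chi-square test named in 10.2 could be run as a one-sample test against 5%. On that view the plan has merely failed to repeat a number.

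It is right that zero is an inference for CPD, and a reader should not take it as the plan's stated intention. But 10.2 gives its comparator without exempting this endpoint, and the neighbouring quit-attempt bullet shows a 5% sizing reference turning into an explicit comparison to zero. A sizing paragraph does not override the analysis rule, and leaving both in place leaves the null open.

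Three further points stand:

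- **Not every outcome is affected.** Mean CPD and the attitude scales have a meaningful no-change null, and feedback items have no baseline.
- **5% is the top of the quoted range.** Section 2.3.3 says participants are not asked to change their smoking, so a lower background is plausible. At 1% the no-change test rarely reaches significance. A near-certain spurious finding holds only near 5%.
- **Abstinence is a weaker case.** A reader might infer that a handful of abstainers would yield a significant cessation result. The documents do not support that: abstinence has no registration measurement, no reference rate in 6.6 and no test assigned to it by name, and it is not among the primary or secondary endpoints.

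**Conclusion.** The conflict is real. The sample size rests on a 5% null for the CPD endpoint, and the analysis text supplies only a baseline that is 0% by definition. The bar falls from 16 of 185 (or 18–19 of 220) to 6 responders. The consequence depends on the true background rate: a 1–2% chance of significance at 1%, 17–28% at 2%, 48–65% at 3% and 90–97% at 5%, across n=185 to n=220. For quit attempts the contradiction between 6.3 and 6.6 is in the text and needs no inference.

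These figures assume a two-sided 0.05 level, exact McNemar (or Fisher) against an all-zero baseline, and 185 or 220 participants analysed. The affected endpoints are secondary; the primary Stage of Change endpoint is untouched. The documents do not support saying that all outcomes are tested against zero, or that the plan writes such a test for CPD or abstinence.

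**What to change.** - In 6.3 and 10.2, state that the day-28 proportion with a CPD reduction of at least 50% is tested against 5% with a two-sided one-sample exact binomial test (or the z-test used for sizing), and reported with its 95% confidence interval. Choose one test in advance, since the threshold at n=220 is 18 or 19 depending on the choice.
- Replace the comparison to zero for quit attempts with a test of the same form against the 5% in 6.6.
- As a minor addition, report 7-day and 30-day abstinence as proportions with 95% confidence intervals, without a test against no change.

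The cost is a few sentences and no new data. Significance becomes harder to reach. With the exact test, power for 10% against 5% is about 76% at n=185 and 78% at n=220; the z-test at n=220 gives about 84%, with an upper-tail error of 0.029. The plan should acknowledge this next to its 80% figure.

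### Section 10.2 names no one-sample test or 5% reference for the two secondary proportions, although section 6.6 sized both as one-sample tests against a fixed 5%

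*Combined protocol and SAP*

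**What the plan says.** Section 10.2 describes the design of every comparison: "Participants will serve as their own controls and comparisons will be made to no change". For numerical data it specifies a one-sample t-test. For categorical data it says that Fisher's "Exact or Chi square tests will be used for categorical data", without saying one-sample and without tying either test to an endpoint. For matched data it adds that "McNemar test will be used for 2-category match-paired data", and it gives Cohen's kappa for three categories. It names no binomial or other one-sample test of a proportion.

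Section 6.3 defines two secondary endpoints at day 28. One is the proportion with at least one quit attempt since starting the sensor, to be compared with zero. The other begins "The proportion of participants who reduced their cigarettes per day (CPD) by" at least 50%, with baseline given as the comparison.

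Section 6.6 uses a different reference. Quit attempts are sized at 25% against 5% (n=16). The CPD reduction is sized at 10%, with n=185 "to show a difference from 5" per cent. Both are sized "using 80% power at a statistical significance of" P<0.05.

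**The concern.** Neither secondary endpoint is a before-and-after pair. A quit attempt since starting the sensor, or a halving of CPD from baseline, has no counterpart at baseline, so McNemar's test does not apply. That leaves the Fisher/chi-square sentence as the only rule in section 10.2 that could govern them. Fisher's exact test compares two independent groups, and this study has one.

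To run Fisher's test, an analyst must supply a second row. The only comparators the text offers are no change, baseline and zero, which give a row of zeros. That row is zero by definition. It is not a sample, and it has nothing to do with the 5% on which the trial was sized. A significant result would then show only that some participants changed, not that more changed than the literature would lead one to expect.

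The CPD endpoint has the largest requirement in section 6.6 (185, against 50 for the primary endpoint and 16 for quit attempts), so it sets the size of the trial.

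**Working it through.** **Inputs.** From section 6.6: reference rate p0 = 0.05; assumed rates p1 = 0.10 (CPD) and 0.25 (quit attempts); power 80%; alpha 0.05. Sidedness is not stated, and two-sided is assumed because it reproduces the plan's figures. Enrolment is up to 220. The attrition rate is not given, so 185 and 220 analysed are both shown.

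**1. Reproduce section 6.6.** For one sample against a fixed rate, with the null variance:

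n = [1.960·√(p0(1−p0)) + 0.842·√(p1(1−p1))]² / (p1−p0)²

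- CPD: [1.960×0.2179 + 0.842×0.3000]² / 0.05² = 0.4619 / 0.0025 = 184.8, so 185. This matches.
- Quit attempts: [1.960×0.2179 + 0.842×0.4330]² / 0.20² = 0.6266 / 0.04 = 15.7, so 16. This matches.

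Other formulas for 10% against 5% do not give 185: one-sided 150, continuity-corrected 205, variance under the alternative 283, two independent groups 435 per group. Section 6.6 is therefore a two-sided one-sample calculation against 5%.

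**2. The test that matches section 6.6, at n=185.** The standard error under 5% is √(0.0475/185) = 0.01602.

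- 15 events (8.1%): z = 0.0311/0.01602 = 1.94, not significant.
- 16 events (8.6%): z = 0.0365/0.01602 = 2.28, significant.

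The exact binomial test has the same cut-off of 16. Power at a true 10% is 76.4% by exact enumeration and 80.0% by the normal approximation. The probability of rejecting at a true 5% is 4.0%.

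**3. Fisher's exact test against the stated comparator, 0/185.** With equal rows, the two-sided P value for k events against none is twice the product of (185−i)/(370−i) for i = 0 to k−1.

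- k = 5: 2×0.0304 = 0.061, not significant.
- k = 6: 2×0.0150 = 0.030, significant.

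So 6 events suffice, and 6/185 = 3.2%, which is below the 5% reference. The probability of 6 or more events is above 99.9% at a true 10% and 90.4% at a true 5%. With 220 analysed against 0/220, the cut-off is still 6 and the probability at a true 5% is 96.6%.

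**4. Side by side, 185 analysed**

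| Test | Events needed | Rejects if true rate is 5% | Rejects if true rate is 10% |
|---|---|---|---|
| One-sample against 5% (goodness-of-fit or exact binomial) | 16 (8.6%) | 4.0% | 76.4% |
| Fisher against 0/185 | 6 (3.2%) | 90.4% | >99.9% |

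Any result from 6 to 15 events (3.2% to 8.1%) would be significant under one reading and not under the other.

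**5. Convention matters at n=220.** The goodness-of-fit chi-square and the minimum-likelihood exact binomial test reject at 18 events (power 84.5%). The equal-tailed exact binomial test rejects at 19 (power 78.1%).

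**The case against.** The strongest reply is that section 10.2 offers Fisher's test or chi-square. A one-sample goodness-of-fit chi-square against 5% suits one group and a fixed rate. It reproduces both sample sizes, and at n=185 it has the same cut-off and power as the exact binomial test. That stands: the plan can be read in a way that loses nothing. But section 10.2 says one-sample for the t-test and not for the chi-square, and it never mentions 5%. The wording it does give points to no change.

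Two further replies have some force. The Fisher/chi-square sentence may be meant for comparisons between participants, such as the two CPD cohorts. If so, section 10.2 assigns no test at all to the secondary proportions. Also, baseline in the CPD endpoint of section 6.3 may only define each person's reduction. In that case section 6.3 gives no reference for the CPD proportion, and the explicit conflict is confined to quit attempts, where zero is stated outright.

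A reader might infer something stronger: that Fisher's test costs the CPD endpoint most of its power. Against a notional 9/185 the power would be 30.3%, and against an independent group of 185 with a true rate of 5% it would be 37.2%. The documents do not support this, because they contain no 5% control group. Those figures belong to an invented comparator, and with the comparator actually stated the error runs the other way.

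Nor should a reader infer that paired yes/no items are at risk. The specific McNemar rule governs them over the general sentence.

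**Conclusion.** The point holds as a mismatch between sections 6.3, 6.6 and 10.2. The trial was sized to show a difference from 5%, and the analysis section states neither that reference nor a test for it. If Fisher's test is followed with the comparator the text does give, the threshold falls from 16 to 6 events of 185, and significance says almost nothing about exceeding 5%. Rejecting zero would not be a false statement in itself. The harm lies in reading it as evidence of more than the benchmark rate.

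The practical weight falls on the CPD endpoint. At the assumed 25%, quit attempts would number about 46 of 185 (0.25×185), well past either cut-off. At the assumed 10%, CPD responders would number about 18 or 19, past both cut-offs but close to 16. The primary endpoint is not affected. This should be corrected, but it is not a reason to question the design.

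The figures assume two-sided alpha of 0.05, 185 or 220 analysed, and a comparator row the same size as the sample for Fisher's test.

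**What to change.** In section 10.2, state that each secondary proportion will be tested with a two-sided one-sample exact binomial test (or a goodness-of-fit chi-square) against the 5% reference in section 6.6, and reported with an exact 95% confidence interval. Name the convention. The equal-tailed binomial test agrees with a Clopper-Pearson interval; the alternatives differ by one event at n=220.

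In section 6.3, replace zero with the same 5% reference for quit attempts. For CPD, keep baseline as the definition of each participant's reduction and add 5% as the reference for the proportion.

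Keep McNemar's test for paired two-category items, and limit Fisher's exact and the two-sample chi-square to comparisons between different participants, such as the CPD cohorts.

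This changes wording only and needs no new data or participants. The price is a higher bar than comparison with zero (16 rather than 6 events of 185) and exact power of 76.4%, slightly under the nominal 80%, if only 185 are analysed.

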#### Exclusion Criteria

- Pregnancy
- Participation in a previous study sponsored by Carrot Inc.

The study will employ non-proportional quota sampling as follows to ensure the study population mirrors the expected initial intended user population:

Age	18-29 years ≤ 20 % of sample	30-60 years Remainder	61-80 years ≤ 10 % of sample
Stage of Change*	Quit 30 days ≥ 20% of sample	Quit 6 months ≥ 20% of sample	Not interested < 20 % of sample
Gender	Male 40-60%	Female 40-60%	
Cigarettes Per Day (CPD)	10-19 CPD 40-60%	≥ 20 CPD 40-60%	
Employment**	Unemployed 4-8% of sample	Employed Remainder	

- \*Stage of Change question and answer choices: Are you seriously thinking of quitting smoking? A. Yes, within the next 30 days B. Yes, within the next 6 months C. No, not thinking of quitting
- \*\* Employment rate among study participants is sought to align with employment rates among the general US population, which currently is 3.7% (Bureau of Labor Statistics, U.S. Department of Labor. The Employment Situation – July 2019. USDL-19-1388. Released August 2, 2019. <https://www.bls.gov/news.release/pdf/empsit.pdf>)

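### Section 10.2 assigns no test to the primary endpoint (Stage of Change, Day 28 against baseline); its only rule for three-category paired data is Cohen's kappa, which measures agreement rather than change

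*Combined protocol and SAP*

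**What the plan says.** **Endpoint.** Section 6.3 sets the primary endpoint as change in the "Stage of Change response at day 28 compared to baseline". It adds a direction: "A positive outcome is defined as a participant responding as more ready to quit". The footnote to the quota table in the same section gives the answer options: "A. Yes, within the next 30 days B. Yes, within the next 6 months C. No, not thinking of quitting". The data are therefore paired, ordered and in three categories.

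**Analysis.** Section 10.2 mentions neither the primary endpoint nor Stage of Change. It sets the general null, "Participants will serve as their own controls and comparisons will be made to no change", and then assigns methods by type of data:

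- a one-sample t-test for numerical variables;
- Fisher's exact or chi-square for categorical variables;
- McNemar for paired data with two categories;
- for the remaining paired case, "Cohen kappa statistic will be used for 3-category match-paired data".

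It also says: "To evaluate changes in attitudes or cigarettes smoked per day over time, repeated measures linear mixed model analyses will be performed". For missing outcomes it separates the two data types: "For categorical data, the last response post-baseline will be carried forward for the day 28 analysis", whereas "Numerical data will use linear mixed modeling".

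**Sample size.** Section 6.6 gives 50 participants for the primary endpoint, from pilot rates of 31% up, 66% unchanged and 3% down at 14 days, with 80% power at the 0.05 level. It names no test.

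**The concern.** An analyst who looks up the rule for paired three-category data in Section 10.2 arrives at kappa, and kappa cannot answer the primary question. It summarises how far the two sets of answers agree beyond chance. Its value stays the same if baseline and Day 28 are swapped, and its usual test (kappa = 0) becomes significant when people keep giving the same answer. Failing to reject would mean that Day 28 answers look unrelated to baseline answers, which is not what the plan means by no change.

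The other listed methods do not clearly fill the gap:

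- **Fisher's exact and chi-square**, as usually applied, test association or compare independent groups. No paired use is specified.
- **McNemar** is limited to two categories, and no two-state version of Stage of Change is defined.
- **The linear mixed model** could show direction, but it needs numeric scores. Section 8 gives 1-10 scales for readiness, confidence and difficulty, and none for Stage of Change.

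An analyst who sets kappa aside must therefore choose a method, and for some methods a scoring or a split, possibly after seeing the data. The study is single-arm and open-label, and its investigators hold equity in the sponsor (Section 11). A pre-specified primary analysis is one of the few safeguards available.

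**Working it through.** **1. The plan's own figure.** Inputs from Section 6.6: up 0.31, down 0.03, 80% power, 0.05 level (taken as two-sided; sidedness is not stated). The sum is 0.34 and the difference d is 0.28. For a McNemar or sign test by normal approximation:

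n = [1.96 × √0.34 + 0.842 × √(0.34 − 0.28²)]² / 0.28² = (1.143 + 0.430)² / 0.0784 = 31.6, so 32.

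With continuity correction n is 39, and by exact calculation 34 (power 80.7%). The stated 50 is not reproduced at 80% power by these tests, so it does not reveal which test was intended. It is larger than they need: exact power at 50 is 95.2%.

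**2. Tables to compare kappa with a test of change.** All cells are assumed, with n = 100. Rows are baseline and columns Day 28, in the order not thinking / 6 months / 30 days. Each table has 66% unchanged, and its baseline mix lies within the Section 6.3 quotas.

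- Improvement: [6, 8, 4; 1, 21, 19; 0, 2, 39], 31 up and 3 down.
- Worsening: the same table transposed, 3 up and 31 down.
- No net change: [10, 6, 2; 6, 26, 9; 2, 9, 30], 17 up and 17 down.

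**3. Kappa** = (po − pe) / (1 − pe), where po is observed and pe chance agreement.

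- Improvement: baseline margins 18/41/41, Day 28 margins 7/31/62. pe = (18×7 + 41×31 + 41×62)/10,000 = 0.394. Kappa = (0.66 − 0.394)/(1 − 0.394) = 0.439.
- Worsening: the margins swap, so po, pe and kappa are identical.
- No net change: pe = (18² + 41² + 41²)/10,000 = 0.369. Kappa = (0.66 − 0.369)/(1 − 0.369) = 0.462 (unrounded pe).

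**4. Change measured directly.** Up minus down is d, with SE = √[(0.34 − d²)/100]. For d = ±0.28 the SE is 0.051; for d = 0 it is 0.058. The exact two-sided sign test on 31 against 3 gives P = 2 × (5984 + 561 + 34 + 1)/2³⁴ = 7.7×10⁻⁷.

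| Table | Kappa | z against kappa = 0 | Up minus down, points (95% CI) | Sign test P |
|---|---|---|---|---|
| Improvement | 0.439 | 6.06 | +28 (18 to 38) | 7.7×10⁻⁷ |
| Worsening | 0.439 | 6.06 | −28 (−38 to −18) | 7.7×10⁻⁷, wrong direction |
| No net change | 0.462 | 6.25 | 0 (−11 to 11) | 1.0 |

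Testing kappa against zero is an assumption, since the plan states no null for it. On that test all three tables are significant, and the largest z belongs to the table with no net movement.

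**5. Dependence on the cells.** A second set of assumed tables gave the same pattern: kappa 0.449 for 31 up and 3 down, 0.449 for its transpose, and 0.493 for a symmetric table with 16 each way. That kappa is unchanged by transposition is algebra and holds for any cells.

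**The case against.** The strongest reply is that the plan comes closer to a usable analysis than this suggests. Section 6.3 lists Stage of Change among the attitudes, and Section 10.2 assigns attitudes over time to a mixed model with F statistics for particular time comparisons. Section 6.6 already sorts participants into up, unchanged and down. On this reading the contrast exists and only a label is missing. This stands in part. The three-way split is written down and the recommended sign test uses it, but Section 6.6 attaches neither a test nor a null to it. The mixed model would show direction: with stages scored 1 to 3, the mean changes in the three tables are +0.32, −0.32 and 0. But no scoring is given, the model is not called primary, and the missing-data rules place categorical outcomes outside it.

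A second reply is that two-sided P values from the sign, Wilcoxon or Stuart-Maxwell tests are also unchanged when the table is transposed. That is true, so symmetry alone does not disqualify kappa. The difference is that the sign test's estimate reverses from +28 to −28, and its null is no net change. Kappa has neither property.

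Third, the answer options come from a recruitment footnote and the questionnaires are redacted, so the Day 28 options cannot be confirmed; there might, for example, be one for people who have already quit. This stands as a caveat. A further option would leave the endpoint still without a named test.

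Finally, the study is low-risk and power is not threatened. Both are true, but neither supplies a primary test.

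**Conclusion.** The concern holds. No test is tied to the primary endpoint, and the one rule that fits its data type yields a statistic with the wrong null and no direction. In the illustration, kappa is 0.44, 0.44 and 0.46 for strong improvement, equally strong worsening and no net change, where the net shift is +28, −28 and 0 percentage points. The cell counts and the test of kappa against zero are assumptions, so these figures show a property of the method and do not forecast the trial's results. The conclusion itself rests on the text of Sections 6.3 and 10.2 and on what kappa measures. The unexplained 50 in Section 6.6 is a separate, smaller gap: it errs on the generous side. The primary test should be settled before the Day 28 data are analysed.

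**What to change.** In Section 10.2:

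- Name one primary analysis. For example, an exact sign (McNemar-type) test comparing the number of participants who moved to a more-ready answer with the number who moved to a less-ready one at Day 28, two-sided at 0.05. A Wilcoxon signed-rank test on the ordered categories would also serve, as would Stuart-Maxwell with the direction reported.
- Report the proportions improved and worsened, and their difference with a 95% confidence interval.
- Keep kappa, if wanted, as a descriptive measure only.
- If the mixed model is meant to cover Stage of Change, state the scoring and label the model secondary.

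In Section 6.6, state which test the 50 refers to. With the sign test at the pilot rates, about 34 participants give 80% power and 50 give about 95%, so enrolment need not rise.

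The cost is a few sentences in 10.2 and one clause in 6.6, with no new data, visits or participants.
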